### 9.1 Evaluating EIMG Adoption

The adoption of EIMG at eligible Prisma Health primary care clinics will be examined through two strategies. First, we will compare key characteristics (e.g., proximity to the PA facilities, number of patients seen, patient insurance distribution, number and type of providers) between clinics that adopt versus those that do not adopt EIMG. Second, during the first month of Phase II, we will seek to conduct semi-structured interviews with practice managers from each Prisma Health primary care clinic that was offered the chance to adopt EIMG, regardless of whether their clinic adopted EIMG or not. The semi-structured interview will be guided by an interview script mapped to the i-PAHRIS framework, exploring decisions to adopt (or not) EIMG at their clinic.

### 9.2 Evaluating EIMG Implementation

Two assessments will be utilized to examine contextual factors influencing the implementation and reach of EIMG at the clinic level. First, we will conduct the Organizational Readiness to Change Assessment (ORCA) with clinic staff (administrators, providers, and staff) at EIMG-adopting clinics. The ORCA tool operationalizes constructs defined in the original PARIHS framework to measure organizational readiness to change in clinic settings. The ORCA consists of three major scales that measure the strength of evidence for the proposed innovation, organizational support for change, and organizational capacity to facilitate the change. In previous work, we adapted and pilot-tested the ORCA as an online questionnaire with Prisma Health primary care clinics (not included in this study) to assess contextual factors related to EIMG adoption and implementation. In the current study, we will conduct the ORCA as an online questionnaire with a representative sample of clinic staff from each clinic after the dissemination of the EIMG Instructional Video (months 2-3) and again after the EIMG Onboard Training (months 6-7).

Second, we will conduct brief (~30 minutes), semi-structured interviews with clinic staff to gain a more nuanced understanding of EIMG implementation across clinics. While self-administered questionnaires or structured interviews cost less and reduce interviewer bias, semi-structured interviews foster rapport and are preferred when seeking information on respondents' attitudes and perceptions on a topic. Semi-structured interviews also allow exploration of issues through extensive probing. The interview scripts will be mapped to the i-PAHRIS framework and structured to complement the quantitative data gained through the ORCA. We will attempt to conduct interviews with a representative sample of staff (e.g., four staff per clinic) approximately 1-2 months after the EIMG Onboard Training (months 6-8).

### **9.3 Evaluating the Effectiveness of the 12-week, Community-Based PA Program**

#### **9.3.1 Changes in Patient PA Levels**

Changes in patient PA levels will be evaluated through two strategies. First, patients will be screened for their PA levels during clinic visits using the PAVS. Patients that enroll in the 12-week PA program will continue to complete the PAVS (to ensure consistency of assessment) at baseline (week 1), midpoint (week 6), conclusion (week 12), and 12 weeks after the completion of the PA program by the EIMG Pros. As a secondary data source, we will extract patient PAVS data from the Prisma Health EHR. We will use this data to monitor patient PA levels prior to receiving the EIMG referral through six months after completing the PA program.

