This multiple case study design will examine the adoption, implementation, and reach of EIMG (i.e., clinic workflow, referral process) across Prisma Health primary care clinics. Twenty Prisma Health primary care clinics will have the opportunity to adopt EIMG beginning in August 2023. Adopting clinics will receive a standardized instructional video and have the EIMG referral process activated, allowing providers to refer eligible patients to the 12-week evidence-informed PA program. In January 2024, adopting clinics will receive an in-depth, tailored EIMG onboard training. At EIMG adopting clinics, we will track referral rates of eligible patients over two phases lasting a total of eight months (months 1-4 after instructional video, months 5-8 after tailored onboard training).

We will use a mixed methods approach to explore factors related to the adoption of EIMG (i.e., characteristics of adopting versus non-adopting clinics), achieving optimal implementation (i.e., clinic workflow, referral process), reach (i.e., proportion of eligible patients receiving a referral, characteristics of referred versus non-referred patients), and patient enrollment in evidence-informed PA programs at participating community PA facilities. The RE-AIM framework will inform the assessment of implementation outcomes, while the i-PARIHS framework will be used to understand contextual factors (i.e., determinants) influencing patient- and clinic-level outcomes. Careful attention will be paid to issues of health equity across all RE-AIM dimensions over the course of the study. Finally, this work will examine the impacts of EIMG implementation on healthcare costs and patient outcomes to assess the cost-effectiveness associated with implementing EIMG in a major health system.

Integrating the EIM model in health systems to connect patients with available community resources has the potential to significantly alter clinical practice and improve population health outcomes. Information gained from this study will lead to the development of a generalizable approach and materials that will inform future implementation strategies on optimizing and scaling up the integration of comprehensive PA models in U.S. health systems. Study findings will also provide cost estimates of potential savings to health systems integrating PA as a population health management tool through clinic-community linkages.

Figure 1. Overall study schematic.

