#### **4.10 Patient Onboarding**

Patient onboarding with EIMG Pros takes approximately one hour and includes completing: 1) appropriate paperwork (i.e., health history forms), 2) pre-participation surveys (i.e., PHQ-9, PROMIS Scale), and 3) measurement of height, body weight (in duplicate), blood pressure (after 10 minutes seated in triplicate), and heart rate (in triplicate). The assessments are also completed at the end of the 12-week program. A rolling enrolment feature allows patients to onboard in <10 business days to maximize readiness for behavior change, with new patients learning from current program participants.

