### 7.2 Prisma Health – Patient Eligibility

Adult patients (≥18 years of age) will be deemed eligible for the study through two different approaches. First, patient eligibility to receive an EIMG referral is determined in real time through a series of steps that are integrated within the patient workflow process in the Prisma Health primary care clinics. Patients that receive an EIMG referral will have the opportunity to enroll in the community-based PA programs and will be considered as the numerator in our ‘reach’ calculations. Second, all patients that were eligible for an EIMG referral (whether they received one or not) at participating clinics will be identified through a retrospective data extraction process from the Prisma Health EHR that will occur at the end of the study period (end of month 8). These broader sample of patients that were eligible for an EIMG referral will be considered as the denominator in our ‘reach’ calculations.

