### 10.0 STUDY TIMELINE

This study will be conducted over three phases: 1) EIMG Adoption; 2) EIMG Introductory Video; and 3) EIMG Onboarding Training. *Phase I* will occur over the first month of this project in which practice managers and their clinic will be offered the opportunity to adopt EIMG, No research activities will take place during this phase. *Phase II* will occur between months 2 through 5, beginning with the dissemination of the EIMG Introductory Video to practice managers and EIMG activation at adopting clinics. This phase will involve several study activities including conducting individual (adoption) interviews with practice managers, clinic staff completing the online ORCA questionnaire, and conducting individual interviews with patients receiving an EIMG referral. *Phase III* will occur from months 6 through 9, beginning with the EIMG onboard training. This phase will involve clinic staff completing the online ORCA questionnaire, conducting individual (implementation) interviews with clinic staff, and continuing the individual interviews with patients receiving an EIMG referral.

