#### 10.1 Timetable - Clinic Assessment of EIMG Referral Pathway

		Month								
	Estimated Time	1	2	3	4	5	6	7	8	9
Practice Manager Assessments										
Individual Interviews (Adoption)	20		X							
Clinic Staff Assessments										
ORCA Questionnaire	10			X	X			X	X	
Individual Interviews (Implementation)	20							X	X	X
Patient Assessments										
Individual Interviews (Enrollment)	30		X	X	X	X	X	X	X	X
EHR Patient Information Extraction	n/a		X	X	X	X	X	X	X	X

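### Section 9.3.1 follows physical activity in the EHR to six months after the program, but every legible extraction date falls before any patient can reach that point

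*Combined protocol and SAP*

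**What the plan says.** Section 9.3.1 describes two sources for changes in patient PA levels. EIMG Pros collect the PAVS from enrolled patients on this schedule: "baseline (week 1), midpoint (week 6), conclusion (week 12), and 12 weeks after the completion of the PA program by the EIMG Pros". The other source, labelled secondary, is the Prisma Health EHR, whose PAVS values are used to "monitor patient PA levels prior to receiving the EIMG referral through six months after completing the PA program".

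The timing of EHR extraction appears in three places:

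- Section 7.2 refers to a "retrospective data extraction process from the Prisma Health EHR that will occur at the end of the study period (end of month 8".
- Section 10.1 has a row "EHR Patient Information Extraction" marked in months 2 to 9. On the Section 10.0 clock, month 1 is the adoption phase, activation opens month 2, and Phase III "will occur from months 6 through 9, beginning with the EIMG onboard training".
- Section 10.3 ties extraction to the end of a phase. Its columns run to month 11, but its cell marks cannot be read in the copy reviewed.

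The synopsis narrative (Section 2.0) gives the tracking window as "months 1-4 after instructional video, months 5-8 after tailored onboard training". On program entry, Section 4.10 states: "A rolling enrolment feature allows patients to onboard in <10 business days". No separate or later EHR extraction for the PAVS is described, and no rule covers patients whose follow-up is still open when data are pulled.

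**The concern.** The follow-up span and the extraction dates are set in different sections and do not fit together. A program of 12 weeks followed by six months takes longer than the whole interval from activation to the last legible extraction. A team following the written schedule would obtain no six-month value for any patient.

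The EHR series is the only source in Section 9.3.1 that runs to six months; facility collection ends 12 weeks after the program. What is at stake is whether the study can say anything about activity six months on. The referral-rate primary outcome is not affected.

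**Working it through.** **Inputs**

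- Program: 12 weeks = 84 days. Follow-up: six months, taken as 26 weeks = 182 days.
- Wait to onboard: 0 to 14 calendar days (Section 4.10, under 10 business days).
- Month = 30.4 days.
- Planned monthly referral rates, constant-step profile of Section 12.3: 0.001, 0.004, 0.007, 0.010, then 0.030, 0.0333, 0.0367, 0.040; sum 0.162.
- Assumed, because the documents do not say: equal numbers of eligible patients each month, and an enrolled share of referrals that does not change over time.

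**1. The window the plan states.** Section 2.0 gives 4 + 4 = 8 months from activation. Section 10.1, months 2 to 9 inclusive, also gives 8 months. 8 × 30.4 = 243 days. The two clocks agree.

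**2. Time needed to reach six months after the program**

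- No wait: 84 + 182 = 266 days from referral.
- 14-day wait: 14 + 84 + 182 = 280 days.

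**3. Shortfall for the earliest possible patient (referred on activation day)**

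- 266 − 243 = 23 days.
- 280 − 243 = 37 days.

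Every later referral falls short by that much plus the days since activation, so the share observable is 0% whatever the referral profile. If month 8 in Section 7.2 is read on the Section 10.0 clock, the pull is 7 × 30.4 = 213 days after activation and the shortfall is 53 to 67 days.

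**4. If the unreadable Section 10.3 table hides a later pull.** Take its last column, end of month 11, with activation opening month 2: 10 × 30.4 = 304 days after activation. Referrals that can reach six months are those made by day 304 − 266 = 38 (no wait) or day 304 − 280 = 24 (14-day wait).

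| Accrual | 14-day wait | No wait |
|---|---|---|
| Constant-step profile | (24/30.4 × 0.001)/0.162 = 0.5% | (0.001 + 7.6/30.4 × 0.004)/0.162 = 1.2% |
| Uniform | 24/243 = 10% | 38/243 = 16% |

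**5. The PAVS 12 weeks after the program (facility data).** This needs 168 to 182 days. The documents do not say when facility collection stops. If it stopped when tracking ends, only referrals made by day 61 to 75 (month 2.0 to 2.5) could reach it, all of them in the video phase:

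- Constant-step profile: 0.0051/0.162 = 3% to 0.0083/0.162 = 5%.
- Accelerated profile of Section 12.3 (0.02 rising to 0.04 after training, sum 0.142): 0.0051/0.142 = 4% to 0.0083/0.142 = 6%.

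**The case against.** The strongest reply is that none of the dates is clearly meant for this extraction. The date in Section 7.2 concerns identifying eligible patients for the Reach denominator, and the table in 10.1 is about the clinic referral pathway. The effectiveness timetable in 10.2 has no EHR row, and the marks in 10.3 are lost. EHR data can be queried retrospectively at any later time, and 9.3.1 states the intended span. This stands in part: a later pull may be intended. But none is written down, and step 4 shows that even the last month displayed in 10.3 would leave the six-month value nearly empty.

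The margin is also narrow. The synopsis mentions a 9-month study period, 9 × 30.4 = 274 days, which exceeds 266 by about 8 days. It would admit only a patient referred in roughly the first week with almost no wait: (8/30.4 × 0.001)/0.162 = 0.2% of planned referrals, or 8/243 = 3% if uniform. No extraction is dated on that clock.

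The EHR PAVS is labelled a secondary source, and neither Section 5.2 nor Section 12.4 names a six-month endpoint. That is correct, and it limits the weight of the point. An early pull shortens the series; it does not remove the physical activity result altogether.

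The remedy overlaps with dating an extraction for the Aim 2 episode of care, but that would not be enough. The episode lasts 120 + 90 = 210 days from the index visit (Section 12.5.2), 56 to 70 days short of the 266 to 280 needed here.

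A reader might also infer that the week-12 values would be few and nearly all from the video phase. The documents do not support this, for two reasons:

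- Those values are collected by EIMG Pros, so an EHR pull date does not by itself cut them off.
- Even if collection stopped at day 243, referrals up to day 145 to 159 would reach week 12. On the constant-step profile that is 0.045/0.162 = 28% to 0.060/0.162 = 37% of referrals. The video-phase share of them is 0.022/0.045 = 49% down to 0.022/0.060 = 37%, a minority. Under uniform accrual the video phase dominates (76 to 84%), but then 60 to 66% of referrals reach week 12, which is not few.

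**Conclusion.** The point holds for the six-month EHR span. On every legible extraction timing no patient can reach six months after the program, and the shortfall is at least 23 to 37 days. This rests only on the plan's own dates and calendar arithmetic; slower onboarding would widen the gap. The month-11 figures (0.5 to 1.2%, or 10 to 16% if uniform) also rest on the accrual assumptions listed above.

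For the facility PAVS 12 weeks after the program, the conclusion is conditional. If collection also ends with tracking, it is reachable only by video-phase referrals from about the first two and a half months, 3 to 6% of planned referrals. The documents leave that open, and no conclusion about the week-12 values follows.

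This should be corrected before data are pulled. It concerns a secondary data source for a secondary aim and does not bear on the primary analysis.

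**What to change.** In Sections 9.3.1 and 10.1, date a separate PAVS extraction from the EHR at least 14 + 84 + 182 = 280 days after the last referral. Reconcile it with Sections 7.2 and 10.3, and state which extraction serves which outcome. State that the six-month value is analysed in enrolled patients whose six-month window has closed by the pull. Also state when facility collection of the 12-weeks-after PAVS ends.

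If no later pull will be made, delete the six-month span from 9.3.1.

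The cost is one more retrospective query and some protocol wording, with no extra patients or visits. The downside is delay: 280/30.4 is about 9.2 months, so this secondary result would arrive about nine months after tracking ends.

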#### **9.3.2 Changes in Patient Health Outcomes**

Primary data for assessing changes in patient health outcomes (i.e., body weight, blood pressure, hemoglobin A1c, lipid profiles) will be extracted from the Prisma Health EHR to allow comparisons between eligible patients that received an EIMG referral and participated in the PA program and eligible patients that do not receive an EIMG referral. Disease incidence, burden, and complications (i.e., the Charlson Comorbidity Index) will be calculated from extracted data.

#### **9.3.3 Individual Interviews with Patients**

As part of our mixed methods approach, we will conduct semi-structured individual interviews, based on the COM-B (Capability, Opportunity, Motivation – Behavior) framework, with patients receiving an EIMG referral. Patients from each of the following three categories will be interviewed: 1) patients who received an EIMG referral from their provider, but chose not to enroll in the PA program, will be queried about their awareness and reasons for not enrolling (i.e., perceived challenges to participation); 2) patients who received an EIMG referral and enrolled, but dropped out, will be asked about their perceptions and satisfaction with the PA program, motivations for enrolling, and reasons for discontinuation; and 3) patients who enrolled and completed the PA program will be queried about their motivations for enrolling, perceptions of and satisfaction with the program, and challenges encountered. Where possible, responses from the individual interviews will be linked to our EIMG implementation strategies, such as clarifying places for additional support and improvements to provider-patient interactions, to add to our comprehensive evaluation of the EIMG referral pathway. We will contact all patients that received an EIMG referral during Phase II (EIMG Introductory Video) to conduct an individual interview. We will conduct a similar number of patient interviews, matching for gender and referring clinic, in Phase III (EIMG Onboard Training).

### 10.0 STUDY TIMELINE

This study will be conducted over three phases: 1) EIMG Adoption; 2) EIMG Introductory Video; and 3) EIMG Onboarding Training. *Phase I* will occur over the first month of this project in which practice managers and their clinic will be offered the opportunity to adopt EIMG, No research activities will take place during this phase. *Phase II* will occur between months 2 through 5, beginning with the dissemination of the EIMG Introductory Video to practice managers and EIMG activation at adopting clinics. This phase will involve several study activities including conducting individual (adoption) interviews with practice managers, clinic staff completing the online ORCA questionnaire, and conducting individual interviews with patients receiving an EIMG referral. *Phase III* will occur from months 6 through 9, beginning with the EIMG onboard training. This phase will involve clinic staff completing the online ORCA questionnaire, conducting individual (implementation) interviews with clinic staff, and continuing the individual interviews with patients receiving an EIMG referral.

#### 10.1 Timetable - Clinic Assessment of EIMG Referral Pathway

		Month								
	Estimated Time	1	2	3	4	5	6	7	8	9
Practice Manager Assessments										
Individual Interviews (Adoption)	20		X							
Clinic Staff Assessments										
ORCA Questionnaire	10			X	X			X	X	
Individual Interviews (Implementation)	20							X	X	X
Patient Assessments										
Individual Interviews (Enrollment)	30		X	X	X	X	X	X	X	X
EHR Patient Information Extraction	n/a		X	X	X	X	X	X	X	X

#### 10.2 Timetable - Evaluating the Effectiveness of the Community-Based PA Program

		Week													
	Estimated Time	0	1	2	3	4	5	6	7	8	9	10	11	12	13
Patient Assessments															
Informed Consent	10	X													X
Participant Intake Form (Demographics)	20	X													X
Anthropometric Biometrics		X													X
Patient Health Questionnaire		X													
Food Behavior Survey		X													X
PROMIS Scale		X													X
Physical Activity Levels		X			X			X		X		X			X
PA Session Participation	2		X	X	X	X	X	X	X	X	X	X	X	X	
PA Exit (Satisfaction) Survey	15														X

\* Note: patients enroll in the 12-week PA program on a rolling basis. The above timetable is relative to their individual enrollment, not the overall study timeline.

### 10.3 Overall Study Timetable

Milestones and Tasks	Month											
	1	2	3	4	5	6	7	8	9	10	11	
Study Start Up												
Hire and train research staff												
Finalizing study protocol and study forms												
Obtaining approval of study documents (i.e., IRB, NIH)												
Register trial with ClinicalTrials.gov												
Establish study databases, finalize study tools												
Finalize the EIMG Instructional Video												
Determine clinics eligible for study participation												
Phase I – Adoption of EIMG												
Email from department chairs to eligible clinics												
Follow up email to clinic practice managers												
Brief, in-person meeting with practice managers												
Phase II – EIMG Instructional Video												
Dissemination of EIMG Instructional Video												
Activation of EIMG to allow EIMG referrals												
Conduct individual (adoption) interviews												
Tracking of EIMG patient referrals for phase II												
Tracking PA program effectiveness												
Begin individual interviews with patients												
EHR data extraction at end of phase II												
Phase III – EIMG Onboard Training												
Conducting standardized EIMG Onboard Training												
Tracking of eligible EIMG patients for phase III												
Conduct individual interviews with clinic staff												
Tracking patient PA program effectiveness												
Continue individual interviews with patients												
EHR data extraction at end of phase II												
Study Wrap Up												
Package and disseminate implementation resources												
Distribute findings to stakeholders/health system												
Manuscript preparation, submission, and publication												
Attend national meetings to present study findings												

